14.2 Adverse Events

14.2.1 Adverse Event Collection Timeframe

The time-period for reporting AEs will be from the time the initial ICF is signed by a participant until completion of the study. This includes events occurring during the screening phase of the study, regardless of whether FLT201 is administered.

14.2.2 Assessments of Adverse Events

Each AE will be assessed in terms of severity, causality, expectedness, and seriousness.

14.2.3 Severity

The medical assessment of severity will be determined by using the definitions specified in [Table 5](#).

Table 5: Adverse Event Severity

Category	Definition
Mild	The AE does not interfere with the participant's daily routine and does not require intervention; it causes slight discomfort
Moderate	The AE interferes with some aspects of the participant's routine, or requires intervention, but is not damaging to health; it causes moderate discomfort
Severe	The AE results in alteration, discomfort or disability which is clearly damaging to health

14.2.4 Causality

The investigator must make the assessment of relationship to ATIMP (FLT201) and NIMP for each AE (prednisolone (prednisone), methylprednisolone and tacrolimus are considered to be NIMPs in this study). The investigator should decide whether there is a reasonable possibility that the event may have been caused by the ATIMP/NIMP. If there is no valid reason for suggesting a relationship, then the AE should be classified as “not related.” Otherwise, if there is any valid reason for suspecting a possible cause-and-effect relationship between the ATIMP/NIMP and the occurrence of the AE, then the AE should be considered “related.” The causality assessment must be documented in the source document(s).

14.2.5 Seriousness

Any AE that meets the criteria for seriousness (see [Table 4](#)) will be documented as such within the source document(s). Hospitalisation for pre-existing conditions, including elective procedures, or a study related procedure (e.g., administration of IV methylprednisolone) does not constitute an SAE.

14.2.6 Expectedness

The reference safety document to be used to assess expectedness against the ATIMP (FLT201) is the IB. Expectedness of AEs are defined in [Table 6](#).

Where an AE is determined as “related” and therefore constitutes an adverse reaction an assessment of expectedness will be determined using the following definitions:

Table 6: Adverse Event Expectedness

Category	Definition
Expected	An AE that is consistent with the information about the ATIMP listed in the IB or clearly defined in this protocol.
Unexpected	An AE that is not consistent with the information about the ATIMP listed in the IB*

Abbreviations: AE=adverse event; IB=investigator's brochure; ATIMP=advanced therapy investigational medicinal product.

* This includes listed events that are more frequently reported or more severe than previously reported.

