6.4 Clinical Data

The study represents the first administration of FLT201 to humans. The same AAVS3 capsid and expression cassette (containing a transgene encoding Factor IX [FIX]) is being administered to humans in an ongoing Haemophilia B program (FLT180a) or expression cassette (containing a transgene encoding α -galactosidase (α -GLA)) in an ongoing Fabry disease program (FLT190). Please refer to the IB for details on clinical experience in FLT180a and FLT190.

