6.5.3.1 Potential Risks Associated with FLT201

Raised ALT and/or a Decline in GCase Expression

ALT elevation is a recognised class event following AAV integration into hepatocytes and represents a loss of transduction efficacy rather than a true safety risk because the transaminase elevation and accompanying decline in expressed protein have, to date, been asymptomatic and self-limited.

To mitigate against the risk of vector-associated transaminitis and subsequent loss of GCase expression (activity and concentration) in this study, participants will be intensively monitored over the course of the study. For further details, see Section [12.2.1](#).

Vector Shedding and Germline Transmission

Following systemic administration of FLT201 there is potential for the spread of vector particles to non-hepatic tissues including the gonads. Therefore, shedding will be assessed in samples taken three times over the first 7-10 days of the study and at each subsequent visit thereafter until no further evidence of AAVS3 is detectable (when samples from all matrices at three consecutive visits are negative). As a precaution, only participants willing to practice birth control methods will be enrolled to avoid the possibility of horizontal, and potentially vertical, transfer of vector. Subjects must refrain from sperm donation for the duration of the trial.

Development of Neutralising Antibodies Against AAV

Experience in animal models indicates that administration of AAV results in a serotype specific stimulation of neutralising antibodies (NAb) production and that such antibodies preclude re-administration of AAV of the same or related, serotype.

Pre-existing anti-AAV humoral immunity is recognised as an important barrier to successful gene transfer through systemic delivery of AAV vectors. To address this challenge, all participants will be screened for pre-existing neutralising antibodies to the AAVS3 vector and excluded if a positive result is returned. A proprietary transduction inhibition assay to measure anti-AAVS3 titres will be performed at a central laboratory.

Development of Anti-GCase Neutralising Antibodies

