In Gaucher disease, the presence of anti-GCase antibodies is not generally considered clinically significant and there is no correlation with safety and efficacy in prior Gaucher disease type 1 development programmes [[Pastores 2016](#)]. The development of de novo anti-human GCase neutralising antibodies would be unexpected in liver directed AAV gene therapy since such liver directed therapy is reported to be immune tolerising for liver expressed and secreted protein. More than 100 patients with haemophilia B have been given gene therapy to date across multiple studies and no inhibitors have been reported [[Arruda 2016](#)]. Therefore, the risk of developing antibodies, with subsequent loss of efficacy from rescue ERT, is thought to be very low, and similar in both previously treated and treatment naïve patients.

Risk of Infusion-related Toxicity

Allergic-type reactions, including anaphylaxis are a rare consequence of administration of biologics. Onset of anaphylaxis is usually rapid following injection of an allergen with 90% beginning within 40 minutes. Patients with a known or suspected intolerance, hypersensitivity, or contraindication to ERT or the investigational product excipients are excluded from the study.

Participants will remain under observation in the investigational centre for at least 8 hours following infusion to minimise the risk associated with acute allergic reaction. Vital signs (pulse, blood pressure, respiration rate, and temperature) will be monitored at 15-minute intervals for the duration of the infusion. Vital signs will be monitored hourly for 6 hours following infusion and then again at 8 hours after the end of the infusion. Infusion reactions should be managed according to [Appendix 1: Suggested Management Guidelines for Infusion Reactions](#).

Myocarditis

Mild, transient myocarditis was observed in the Phase 1/2 study of FLT190 in subjects with Fabry disease. FLT190 consists of the same proprietary AAVS3 capsid however includes a different transgene which encodes α galactosidase. See the FLT201 Investigator Brochure for further details.

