14.1 Adverse Event Definitions

Adverse event (AE) definitions are provided in [Table 4](#).

Table 4: Adverse Event Definitions

Term	Definition
Adverse event	Any untoward medical occurrence in a clinical investigation participant administered a pharmaceutical product that does not necessarily have a causal relationship with the treatment
Adverse reaction	All untoward and unintended responses to an investigational medicinal product related to any dose administered
Serious adverse event	Any AE that: 
 • results in death, • is life-threatening*, • requires hospitalisation** or prolongation of existing hospitalisation, • results in persistent or significant disability or incapacity or consists of a congenital anomaly or birth defect. • is considered an important medical event (defined below)
SUSAR	A suspected unexpected Adverse Reaction which is also categorised as serious
Important medical event	These events may jeopardise the participant or may require an intervention to prevent one of the above characteristics/consequences. Such events should also be considered “serious.” See Section 14.3.8 for study-specific events that should also be considered as important medical events

Abbreviations: AE=adverse event; SUSAR=suspected unexpected serious adverse reaction.

* A life-threatening event refers to an event in which the participant was at risk of death at the time of the event; it does not refer to an event which hypothetically might have caused death if it were more severe.

** Hospitalisation is defined as an in-patient admission, regardless of length of stay. Hospitalisation for pre-existing conditions, including elective procedures do not constitute an SAE.

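### Table 6 lets the protocol as well as the IB make an event expected, so a related serious event defined only in the protocol is both expected and unexpected and its SUSAR status is undetermined

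*Protocol*

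**What the plan says.** Protocol section 14.2.6 opens by naming one reference: "The reference safety document to be used to assess expectedness against the ATIMP (FLT201) is the IB". Table 6, in the same section, then gives two definitions.

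- The first row, for expected events, has two alternatives: "An AE that is consistent with the information about the ATIMP listed in the IB or clearly defined in this protocol".
- The second row, for events to be treated as unexpected, leaves the protocol out and reads: "An AE that is not consistent with the information about the ATIMP listed in the IB". A footnote on this row adds: "This includes listed events that are more frequently reported or more severe than previously reported".

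Table 4 in section 14.1 defines a SUSAR as "A suspected unexpected Adverse Reaction which is also categorised as serious".

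The protocol also describes several events in advance, although section 6.4 states: "The study represents the first administration of FLT201 to humans". Section 6.5.3.1, on risks associated with FLT201, says "ALT elevation is a recognised class event following AAV integration into hepatocytes" and, further on, "Mild, transient myocarditis was observed in the Phase 1/2 study of FLT190 in subjects with Fabry disease". Section 14.2.9 makes specified ALT rises and myocarditis adverse events of special interest.

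The SAP has SUSAR in its abbreviation list and plans no summary by expectedness.

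**The concern.** The two rows of Table 6 should divide related events into two groups with no overlap. They do not, because one row draws on the IB and the protocol and the other on the IB only. The wider row also disagrees with the sentence that introduces the table.

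In a first-in-human study, a protocol often describes an event because it is to be watched for, not because it is an established reaction to the product. If that description is enough to make the event expected, a serious related case can be left out of SUSAR classification. Two assessors applying the same table could also classify the same case in opposite ways. Enrolment is approximately 18, with participants dosed at least 4 weeks apart, so a single case may carry much of the information on a given risk.

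**Working it through.** No arithmetic applies. The check compares section 14.2.6, both rows and the footnote of Table 6, and the SUSAR definition in Table 4.

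**Step 1: classify a related serious event by where it is described.**

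| Where described | Expected row | Unexpected row | Lead sentence of 14.2.6 (IB) | SUSAR under Table 4 |
|---|---|---|---|---|
| IB, at the severity and frequency seen before | applies | does not apply | expected | no |
| IB, but now more severe or frequent; not in protocol | does not apply | applies (footnote) | unexpected | yes |
| Protocol only | applies | applies | unexpected | depends on the row used |
| IB, but now more severe or frequent; also in protocol | can apply through the protocol | applies (footnote) | unexpected | depends on the row used |
| Neither | does not apply | applies | unexpected | yes |

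The third and fourth lines are the defect. Nothing elsewhere in the protocol says which row prevails.

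**Step 2: check the wording of the Expected row.** It can be read in two ways. Either the event must be consistent with information about FLT201, found in the IB or the protocol, or it is enough that the event is clearly defined in the protocol. Both readings admit the protocol as a source, so the third line stands either way. The fourth line needs the second reading, because the first keeps a consistency test. The footnote on severity and frequency speaks of listed events and is attached to the Unexpected row, so the protocol route carries no such limit of its own.

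**Step 3: see which events could be affected.**

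- ALT elevation or transaminitis is the clearest candidate. Section 6.5.3.1 presents it as a class event, section 13.2 says it is anticipated, and section 14.2.9 defines it by criteria. One limit applies: section 14.2.5 says that hospital admission for a study-related procedure, such as giving IV methylprednisolone, is not an SAE. The case would have to be serious on other grounds.
- Myocarditis is a possible candidate. It is an AESI and stands under the FLT201 risk heading, but the text rests on mild, transient cases with another product that has the same capsid. Section 6.5.3.1 refers to the FLT201 IB for details, so the IB discusses it. Whether it is listed there as an expected reaction, and at what severity, cannot be seen.

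**Step 4: list what applies whatever the classification.**

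- All SAEs and AESIs go from the investigator to pharmacovigilance within 24 hours (14.3.1, 14.2.9).
- Enrolment is held for a related death, a related malignancy, neutralising antibodies meeting the stated criteria, or a related severe event that is life-threatening or needs urgent intervention (13.6). Investigators, authorities and ethics committees are then told (13.7).
- Severe related events are DLTs, except ALT or AST rises without a bilirubin increase (13.2).
- At least 4 weeks of data are assessed before each dosing (13.3.1), and the DMC reviews before escalation or expansion (13.1.1).
- Section 14.3.10 sets 7- and 15-day reporting for certain other safety events and cites the EU and US reporting rules.

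None of these says how expectedness is decided. A related myocarditis that leads to hospital admission, without being life-threatening or needing urgent intervention, meets no listed halt criterion. For such a case the choice of row affects onward reporting.

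**The case against.** The strongest reply is that this is loose drafting with little reach. On a natural reading, the protocol alternative covers information about FLT201, and a list of AESIs, important medical events or halt criteria is not a statement that FLT201 causes those events. Most serious cases would also be caught by the rules in step 4.

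Much of this stands. A reader might infer that every risk named in the protocol can be downgraded, including malignancy, anaphylaxis and anti-GCase neutralising antibodies. The documents do not support that:

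- Section 6.5.3.1 itself says that de novo neutralising antibodies would be unexpected.
- Malignancy is not described there as an FLT201 risk. Section 6.5.3.2 links it to tacrolimus; otherwise it appears as a halt criterion and an important medical event.
- Allergic-type reactions are described as a rare consequence of biologics in general, and Appendix 1 calls acute infusion reaction highly unlikely. Section 14.3.8 sends severe related allergic reactions through SAE reporting in any case.

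A reader might also infer that serious events could go unreported while dosing continues. Step 4 rules that out for reporting to pharmacovigilance, and for notice to authorities when a halt criterion is met.

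The objection does not remove the conflict between the two rows. If the protocol alternative was meant only for transaminitis, the table does not say so.

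**Conclusion.** The point holds as an internal contradiction. Table 6 is not mutually exclusive and disagrees with its own lead sentence, and SUSAR status under Table 4 depends on how that is resolved. The table permits a protocol-defined event to be classed as expected; it does not require it.

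The size rests on an assumption about the IB, which is not in the documents. If the IB lists ALT elevation and myocarditis at the relevant severity, the effect is nil. If it lists neither, serious related cases of both could be left out of SUSAR classification. The harm is confined to onward SUSAR reporting. No planned SAP table changes. The documents do not show whether any related SAE has yet been assessed under this table.

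This should be corrected, because it is a stated safety-reporting rule that is wrong as written, in a first-in-human gene therapy study, and the correction is small.

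**What to change.** 1. Delete the last six words of the Expected row in Table 6, so that both rows use the IB, as the lead sentence of section 14.2.6 does.
2. Add a sentence to section 14.2.6: naming an event in the protocol as a risk, AESI, important medical event or halt criterion does not by itself make it expected.
3. Re-check the expectedness of any related SAEs already assessed.

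The cost is a short amendment, a review of whatever related SAEs exist, and possibly a few more expedited reports. No dose, endpoint or analysis changes. If the IB already covers these events, nothing is lost.

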14.2.7 Follow-up of Adverse Events

All AEs must be followed to conclusion regardless of whether the participant is still participating in the study. Conclusion can be that the event has resolved or until, in the opinion of the investigator, the event has stabilised or been determined to be chronic. The follow-up must be documented in the source document(s).

14.2.8 Reporting of Adverse Events

All AEs and SAEs are collected from the time the ICF is signed until Week 38/EOS visit.

Where possible, a diagnosis rather than a list of symptoms should be recorded. If a diagnosis has not been made, then each symptom should be listed individually. All AEs should be captured on the appropriate AE pages in the eCRF and in source documents. In addition to untoward AEs, unexpected benefits outside the investigational product indication should also be captured on the AE eCRF.

14.2.9 Adverse Events of Special Interest (AESI)

The following will be considered as AESIs:

- Any of the following related to ALT elevation:
 - Increase of ALT above normal on one occasion (if normal at baseline)
 - >50% increase of ALT from baseline on one occasion followed by a further increase from the prior level at the next blood test (at same laboratory)
 - Increase in ALT associated with unexpected fall in plasma GCase activity level.
- Unplanned increase in immunosuppression- an increase in immune suppression includes an increase in dose or duration or number of drugs used above the existing prophylactic and reactive regimens.
- A positive test result for SARS-CoV-2 (COVID-19) infection.
- An increase in hs troponin-T to greater than twice the upper limit of normal (normal troponin-T is <14 pg/mL).
- A change in 12-lead ECG deemed clinically significant by the investigator.
- Myocarditis.

Any events meeting the definition of an AESI should also be reported by the investigator to PPD Pharmacovigilance Department via the same process as reporting SAE, see Section 3 (SAE [contact], SAE Faxline [contact]) within 24 hours of the first awareness of the event. In the event of that Medidata RAVE project database is not available, use the SAE form and highlight that the event is an AESI. The CRF of Medidata RAVE must be updated as soon as it is available.

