9.2 Exclusion Criteria

Patients will not be eligible to participate in the study if they meet any of the following exclusion criteria:

1. Diagnosed or suspected type 2 or type 3 Gaucher disease (including any patient with eye movement abnormality on clinical examination).
2. Positive for neutralising antibodies to AAVS3 at screening.
3. Evidence of significant and persistent liver dysfunction at Screening defined as > 1.5 x upper limit of normal (ULN) in alanine aminotransferase (ALT), aspartate aminotransferase (AST) or total bilirubin.
4. Evidence of any of the following at screening:
 - a. Hb < 8 g/dL.

- b. Platelets $<45,000/\text{mm}^3$.
 - c. Pulmonary hypertension.
 - d. New osteonecrosis within 12 months of screening.
 - e. Fragility fracture or bone crisis within 12 months of screening.
5. Hepatitis B surface antigen (HBsAg) positive at screening.
 6. Hepatitis C antibody (Hep C Ab) positive and hepatitis C RNA polymerase chain reaction (PCR) (as follow-up test if Hep C Ab-positive)-positive at screening.
 7. Cytomegalovirus (CMV) immunoglobulin G (IgG) and CMV DNA PCR-positive at screening.
 8. Human immunodeficiency virus (HIV)-1 or -2 antibody positive at screening.
 9. Receipt of live attenuated vaccination within 12 weeks prior to screening or intends to receive such vaccination during the study.
 10. History of clinically-advanced liver disease e.g., cirrhosis, portal hypertension.
 11. History of bone marrow transplant.
 12. History of splenectomy (partial or total).
 13. History of splenic infarct within 12 months of screening.
 14. History of receiving any gene transfer medicinal product.
 15. History of receiving any investigational therapy for Gaucher disease within 60 days of screening.
 16. Participation in any other clinical study of an investigational medicinal product (IMP), and/or receiving any other IMP during the study.
 17. History of idiopathic thrombocytopaenic purpura, thrombotic thrombocytopaenic purpura, thrombocytopaenia, anaemia, hepatomegaly, splenomegaly, and/or osteoporosis, unrelated to Gaucher disease.
 18. History of, or active neoplastic disease within 5 years of screening (except for basal or squamous cell carcinoma of the skin or carcinoma in situ which has been definitively treated).
 19. History of uncontrolled cardiac failure, unstable angina, or myocardial infarction or other acute cardiac conditions requiring clinical management in the past 6 months.

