10.4 Immunosuppression Management

As noted in Section 6.5.3.1, liver-directed gene therapy with an AAV-based capsid has been reported to be associated with a likely T-cell mediated immune response to vector-transduced hepatocytes resulting in rises in liver transaminase levels, most notably ALT.

For all participants, LFTs will be closely monitored (Section 12.2.1) to enable timely identification and treatment of episodes of breakthrough ALT increase to preserve GCase expression (activity and concentration).

Participants will receive a prophylaxis regimen (post-dosing with FLT201) starting at approximately Week 3 post-dosing, continuing for a duration of up to approximately 3 weeks at the initial dose followed by a taper over 11 to 13 weeks.

The prophylaxis regimen consists of oral steroid (prednisolone/prednisone) and/or oral tacrolimus. An appropriate quantity of steroid and/or tacrolimus will be dispensed to the participant to cover the period between clinic visits and usage will be monitored via tablet counts.

In the event of breakthrough elevation of liver transaminase, participants will be assessed by the treating physician, and a reactive regimen (consisting of IV methylprednisolone) may be initiated in accordance with the CIMP.

The CIMP provides detail of the prophylaxis and reactive regimens, as well as more detailed guidance regarding the assessment and management in case of observed ALT elevation. The CIMP will be available to the investigator, pharmacy, and key study personnel. If the investigator considers that any systemic immune-modifying medication other than those prescribed in accordance with the CIMP may be necessary, this should be discussed with the Medical Monitor and Sponsor.

Any significant changes in the CIMP will be reviewed by the DMC, and changes may be issued as an update to the CIMP and communicated to all sites. If the DMC considers that significant changes are required, such as addition of other drugs (i.e., additional NIMP), then a protocol amendment may also be submitted.

11 Concomitant Medication

All non-study treatment received within 30 days prior to initial informed consent and for the duration of the study must be recorded on the appropriate eCRF page. Concomitant medication includes prescription and non-prescription medication and herbal treatments. Concomitant medication also includes immunosuppressants used as part of an immune management and monitoring regimen as described in the CIMP.

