#### **9.1.7. Adverse Events of Special Interest (AESI)**

AESIs are defined in the protocol. AESIs will be summarized by SOC, preferred term, study part, dose cohort, and overall.

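### With ALT above normal at baseline, a large one-interval ALT jump can miss the AESI definition, while any crossing above normal from a normal baseline meets it

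*Protocol*

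**What the plan says.** Protocol Section 14.2.9 gives three alternative ALT criteria, any one of which is enough:

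1. "Increase of ALT above normal on one occasion (if normal at baseline").
2. ">50% increase of ALT from baseline on one occasion followed by a further increase from the prior level at the next blood test", with both tests at the same laboratory. It is not restricted by baseline status.
3. "Increase in ALT associated with unexpected fall in plasma GCase activity level". It is not restricted by baseline status either.

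A separate item covers an unplanned increase in immunosuppression, where "an increase in immune suppression includes an increase in dose or duration or number of drugs used above the existing prophylactic and reactive regimens". Planned treatment falls outside that item: under Protocol Section 10.4, after a breakthrough rise "a reactive regimen (consisting of IV methylprednisolone) may be initiated in accordance with the CIMP", the CIMP being the Clinical Immune Management Plan.

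Exclusion criterion 3 (Protocol Section 9.2) reads "Evidence of significant and persistent liver dysfunction at Screening defined as > 1.5 x upper limit of normal (ULN") and covers ALT, AST and total bilirubin. ALT above 1.0 and up to 1.5 × ULN is therefore compatible with enrolment. Section 14.2.9 does not define baseline; SAP Section 4 uses the latest available value before infusion.

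AESIs must be reported within 24 hours. SAP Section 9.1.7 adopts the definition unchanged: "AESIs are defined in the protocol. AESIs will be summarized by SOC, preferred term, study part, dose cohort, and overall".

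**The concern.** The one-occasion criterion is closed to participants who start above normal. For them no ALT value, however high, is an AESI on ALT alone unless the next test at that laboratory is higher still. A participant who starts normal qualifies on any single value above the limit, however small the rise.

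Raised ALT is the first risk listed in Protocol Section 6.5.3.1, and other fast reporting routes are narrow for it. Section 13.2 excludes ALT or AST rises without a bilirubin rise from the dose-limiting toxicity (DLT) definition. Section 14.2.5 says that hospitalisation to give IV methylprednisolone is not in itself an SAE. AESI status is therefore a main route to a 24-hour report. Section 13.2 also asks for the prophylactic regimen to be reconsidered before further participants are treated when a vector-associated ALT or AST rise is severe, so timing matters. In the AESI table, incidence by dose cohort would depend partly on how many participants started above normal.

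**Working it through.** The plan gives no figure to reproduce, so the check applies the written rule to example series. Only the thresholds come from the documents; the ALT series are illustrative.

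**Rule.** Let B be baseline ALT and x1, x2, … successive values at one laboratory, all in multiples of ULN.

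- Criterion 1: B ≤ 1 and some x > 1.
- Criterion 2: some x > 1.5 × B, and the next x is higher.
- Criterion 3: ALT rises and plasma GCase falls unexpectedly.
- Immunosuppression item: treatment exceeds the planned prophylactic and reactive regimens.

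**Series.** GCase is stable and treatment is within the planned regimens unless noted.

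| B, then successive values | 1.5 × B | First rise over baseline | AESI? |
|---|---|---|---|
| 0.98, then 1.02, 0.95 | – | 1.02/0.98 = 1.04 (+4%) | Yes, criterion 1 |
| 0.9, then 8, 5 | – | 8/0.9 = 8.89 (+789%) | Yes, criterion 1 |
| 1.4, then 7.0, 6.5 | 2.1 | 7.0/1.4 = 5.0 (+400%) | **No**: 6.5 < 7.0 |
| 1.2, then 8, 5, 2 | 1.8 | 8/1.2 = 6.67 (+567%) | **No**: 5 < 8 |
| 1.5, then 10, 6 | 2.25 | 10/1.5 = 6.67 (+567%) | **No**: 6 < 10 |
| 1.2, then 8, 5, 2, with unexpected GCase fall | 1.8 | +567% | Yes, criterion 3 |
| 1.2, then 8, 5, 2, with treatment beyond the reactive regimen | 1.8 | +567% | Yes, immunosuppression item |
| 1.2, then 3, 8, 5 | 1.8 | 3/1.2 = 2.5 (+150%) | Yes, criterion 2: 3 > 1.8 and 8 > 3 |
| 1.4, then 2.5, 7.0, 6.5 | 2.1 | 2.5/1.4 = 1.79 (+79%) | Yes, criterion 2: 2.5 > 2.1 and 7.0 > 2.5 |

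**Conditions for a miss.** All four must hold:

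- baseline ALT is above normal;
- no value above 1.5 × B is followed by a higher one at the same laboratory, so ALT passes from at most 1.5 × B to its peak within one sampling interval;
- there is no unexpected GCase fall;
- treatment stays within the planned regimens.

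**Sampling interval.** Local liver tests run twice weekly in Weeks 1–9 and 28–38 (7/2 = 3.5 days) and three times weekly in Weeks 10–27 (7/3 = 2.3 days). Protocol Section 12.2.1 asks for additional tests during a suspected episode, which could shorten the gap.

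**Effect on the table.** One reclassified participant moves cohort AESI incidence by 1/3 = 33 percentage points in a cohort of 3, or 1/2 = 50 points in a cohort of 2. This is arithmetic for one hypothetical case, not an estimate.

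**The case against.** Much of the opposing case stands.

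- **A second rise is not always needed.** A reader might infer that it is for anyone with raised baseline ALT. Criterion 3 applies at any baseline without one, and Section 12.2.1 asks for a weekly extra GCase sample while liver tests are raised, so it can be assessed. The immunosuppression item is a further route.
- **Most gradual rises are caught.** Any rising pair of tests that starts above 1.5 × B meets criterion 2, and the first of the pair need not be the peak.
- **Dependence on treatment is not shown.** A reader might infer that the faster a flare responds, the less likely it is to be counted. That assumes treatment starts and lowers ALT before the next test. Section 10.4 says only that the reactive regimen may be started, the CIMP is not among the documents, and no response times are given.
- **The event is not lost.** Clinically significant changes are reported as AEs (Protocol Section 12.5.3). SAP Section 9.6.1 summarises and lists liver tests and plots ALT by participant and laboratory. The data monitoring committee reviews participant data before escalation or expansion.
- **Confirmation is a legitimate choice.** When ALT is already raised, requiring a second rise trades sensitivity for fewer false alarms.

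The last argument is weakened by criterion 1, which accepts an unconfirmed crossing of any size from a normal baseline. None of these points brings the single-interval jump with stable GCase and planned treatment into the definition.

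**Conclusion.** The gap is real but narrow. With baseline ALT above normal, a rise of any size is an AESI only if the next same-laboratory test is higher, plasma GCase falls unexpectedly, or immunosuppression goes beyond the planned regimens. A one-interval jump that meets none of these misses 24-hour AESI reporting and the SAP 9.1.7 table. It does not go unrecorded.

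Its practical size cannot be computed, because the documents do not say how many participants start above normal. A reader might infer that AESI rates across dose cohorts are materially distorted; nothing in the documents establishes that, and the analysis is descriptive. The conclusion rests on reading Section 14.2.9 literally, on SAP Section 4 for baseline, and on treatment under the CIMP counting as planned. SAP Section 1 refers to several regional protocols; only version 8.0 was available. The change is worth making because it is cheap and concerns prompt reporting of the first-listed risk.

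**What to change.** In Protocol Section 14.2.9, keep the three ALT criteria and add a fourth: *in a participant whose ALT is above normal at baseline, a single ALT value more than 50% above that baseline*. The three missed series then qualify: 7.0 > 2.1, 8 > 1.8 and 10 > 2.25.

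The addition should not replace criterion 2. That criterion also catches rises within the normal range, such as 0.4 to 0.65 to 0.8 × ULN (0.65 > 0.6 and 0.8 > 0.65), which restricting it to raised baselines would drop.

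Optionally, also make an ALT rise for which the reactive regimen is started reportable as an AESI. This is a reporting trigger only and changes no treatment.

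For data already collected, derive the revised definition by program and show it in a labelled supplementary table beside the protocol-defined SAP 9.1.7 table, not in place of it. That keeps AESIs under the existing definition separate from laboratory flags defined later.

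The cost is amendment wording, some programming on ALT data already collected, and some extra AESI reports. These would include modest or isolated fluctuations: 1.4 to 1.9 to 2.3 to 2.2 × ULN would newly count, since 2.3 > 2.1 (2.3/1.4 = 1.64, +64%).
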